7.1.1.1 Temporary Discontinuation

Study drug administration may be stopped temporarily (up to 21 days) due to AE(s) and will be restarted after the AE resolves to Grade 1. If an AE has not resolved after this period, but the Investigator confirms there is clinical benefit for the patient to continue study participation, this period could be extended upon discussion with Medical Monitor and Sponsor. If the AE still has not resolved after this extended period, and no clinical benefit was confirmed then the patient will be discontinued from study drug.

7.1.2 Dose Escalation Rules and Safety Steering Committee

A dose in which the safety stopping criteria have been met (Section 7.1.1) or where toxicity was observed based on the DLT assessment criteria (Section 7.1.2.2) will not be repeated and further dose escalation will not occur. Where stopping criteria have not been met, the decision of the SSC may be to give the next intended dose, a smaller than the predefined dose increment, a repeated dose or to stop dosing. There will be a temporary halt for enrollment after the first 3 patients are enrolled in each cohort until the SSC clears that the dose level is safe to continue the dose escalation.

Measures to ensure data integrity and safety of patients will be detailed in the Data and Safety Monitoring Plan.

If the Investigator, the Medical Monitor or the Sponsor becomes aware of conditions or events that suggest a possible hazard to patients if the clinical study continues, then the clinical study may be terminated after appropriate consultation among the involved parties. The clinical study may be terminated at the Sponsor's discretion also in the absence of such a finding.

Should the study be terminated, and/or the study center closed for whatever reason, all documentation pertaining to the study and study drug must be returned to Sponsor. Any actions of the study site required for assessing or maintaining patient safety will continue as required, despite termination of the study by the Sponsor.

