4.1.1 Part 1 (Dose Escalation)

Approximately 30 patients with any solid tumor who require low-dose EBRT will be enrolled sequentially to the four planned NOX66 dose groups (Dose Cohort 1: 800 mg [3 to 6 patients]; Dose Cohort 2: 1200 mg; Dose Cohort 3: 1600 mg; Dose Cohort 4: 2400 mg [3 to 8 patients in each of Dose Cohorts 2 to 4]; total daily dose administered twice a day [BID]). At least 2 patients enrolled in Dose Cohorts 2 to 4 must have mCRPC.

The proposed dose regimen for Part 1 is given in Table 4-1. No intra-subject dose escalation is allowed.

	Dose Cohort					
	1	2	3	4		
Total daily dose	800 mg	1200 mg	1600 mg	2400 mg		
Dosing regimen	400 mg BID	600 mg BID	800 mg BID	1200 mg BID		
Number of suppositories per day	$2 \times 400 \text{ mg}$	2 × 600 mg	$4 \times 400 \text{ mg}$	4 × 600 mg		

Table 4-1Proposed Doses for NOX66 (Part 1)

BID = twice daily

All patients will be closely monitored for any dose-limiting toxicities (DLTs) up to Day 21 of Cycle 1.

Dose escalation will be based on an adapted "3+3" design, where dose cohorts will be expanded for up to 6 patients (Dose Cohort 1) in the event of DLT or up to 8 patients (Dose Cohorts 2 to 4) to allow for robust estimation of PK parameters after being deemed "safe" based on the traditional "3+3" design.

At each dose level, 3 patients will initially be treated with NOX66.

- If none of the first 3 patients enrolled in Cohort 1 experience a DLT during the first treatment cycle, the dose will be escalated to the next level.
- If none of the first 3 patients experience a DLT during the first treatment cycle of Cohorts 2 to 4, then the dose level will be deemed "safe" and up to 5 additional patients will be enrolled to the current dose level for estimation of PK parameters. At the same time (with the exception of Cohort 4), the next dose level will be initiated and the first 3 patients will be enrolled to the escalated dose.
- If 1/3 patients experience a DLT, an additional 3 patients will be enrolled. If 1/6 patients experience a DLT then this dose level will be deemed "safe" and, for Cohorts 2 to 4, 2 more patients may be enrolled for estimation of PK parameters. At the same time, the next dose level will be initiated and the first 3 patients will be enrolled to the escalated dose.
- If > 1/3 or > 1/6 patients experience a DLT, then dose escalation will be halted, and the previous dose will be declared as the MTD.

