7.1 Discontinuation of Study Drug

7.1.1 Safety Stopping Criteria:

It may be necessary for a patient to permanently discontinue (definitive discontinuation) study drug. If study drug is definitively discontinued, the patient will remain in the study to be evaluated for clinical observation and safety monitoring. See the SoA (Table 1-1 [Parts 1 and 2]) for data to be collected at the time of discontinuation of study drug and follow-up and for any further evaluations that need to be completed.

Patients may be discontinued from study drug in the following situations:

- Patient decision. The patient free to discontinue study drug at any time, without prejudice to further treatment.
- Any AE that in the opinion of the Investigator or Sponsor contraindicates dosing or meets the criteria for discontinuation.
- Recurrence of the same Grade 3 AE, even if recurrence is at a lower dose of study drug, with the exemption of localized skin reactions associated with drug administration which responds to topical corticosteroids.
- Unacceptable toxicity.
- Severe noncompliance with the protocol.
- Disease progression or unacceptable toxicity.
- Patient started alternative anticancer therapy including another investigational agent.
- Patient is lost to follow-up.

For patients with mCRPC, study drug will not be stopped due to rises in PSA alone. The Prostate Cancer Working Group 3 (PCWG-3) emphasized the importance of keeping patients on the study until radiographic or symptomatic progression, which better reflects the clinical course.

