For each dose escalation cohort, additional patients may be enrolled or replaced if a patient discontinues prior to the completion of Cycle 1 for reasons other than safety. Patients who develop a DLT and discontinue treatment will not be replaced.

If a patient develops any DLT during Cycles 2 to 6, these will be considered 'DLT equivalent toxicity' and will be recorded in the eCRF. This information may be considered during SSC review to assess dose escalation.

When a DLT occurs, the site must immediately inform Parexel who will then inform the other sites that a DLT has occurred and evaluate if a second DLT has occurred at any other sites.

Assessment of toxicities and decisions about dose recommendation for Part 1 (dose escalation) will be made during the SSC meeting.

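### Section 7.1.2 closes a dose level after any DLT, with no patient count, while Section 4.1.1 repeats the dose after 1/3 and halts only at two or more DLTs

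*Combined protocol and SAP*

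**What the plan says.** **Section 7.1.2** opens with two triggers. The sentence begins "A dose in which the safety stopping criteria have been met (Section 7.1.1" and then adds a dose where "toxicity was observed based on the DLT assessment criteria (Section 7.1.2.2) will not be repeated and further dose escalation will not occur". Neither trigger carries a patient count. The next sentence makes the Safety Steering Committee's options conditional: "Where stopping criteria have not been met, the decision of the SSC may be to give the next intended dose". The other options it lists are a smaller increment, a repeat of the dose, or stopping.

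**Section 4.1.1** works by counts: "If 1/3 patients experience a DLT, an additional 3 patients will be enrolled". One DLT in six means that the level is deemed safe and the next one opens. Then: "If > 1/3 or > 1/6 patients experience a DLT, then dose escalation will be halted". It also describes 1200 mg as not tolerable at two or more patients with DLTs. The synopsis repeats these rules. Table 3-1 (MTD and RP2D) and Section 9.4.6.1 accept at most one patient in six with a DLT.

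**Section 7.1.2.2**, to which the DLT trigger points, defines a DLT in one patient during Cycle 1 and sets no cohort threshold. Of DLT-type toxicity in Cycles 2 to 6 it says: "This information may be considered during SSC review to assess dose escalation".

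**Section 7.1.1**, to which the other trigger points, introduces its list with "Patients may be discontinued from study drug in the following situations". One item is "Recurrence of the same Grade 3 AE, even if recurrence is at a lower dose of study drug", with an exemption for local skin reactions that respond to topical corticosteroids. Other items are patient decision, severe noncompliance, disease progression, start of another anticancer therapy and loss to follow-up.

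**The concern.** The same observation, one DLT at a dose level, leads to opposite mandatory actions depending on which section is read. MTD and RP2D are the Part 1 primary objective, and every Part 2 patient is treated at the RP2D, so the choice of section carries through to the rest of the study.

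A hypothetical case: one DLT among the first three patients at 1600 mg, none in the next three. Section 4.1.1 deems 1600 mg safe and opens 2400 mg. Section 7.1.2 closes 1600 mg at the first DLT, so the second three are never enrolled and 1200 mg is the highest dose left to carry forward. No text says which section prevails. Whichever the committee follows, it departs from the other.

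**Working it through.** **1. The rules side by side**

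| DLTs at a level | Section 4.1.1 | Section 7.1.2 as written | Agree? |
|---|---|---|---|
| 0/3 | Cleared | No bar from DLTs | Yes |
| 1/3 | Enrol 3 more at this dose | Dose not repeated, escalation ends | No |
| 1/6 | Deemed safe, next level opens | Already closed at 1/3 | No |
| 2 or more | Halt | Closed | Yes |

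The conflict is confined to exactly one DLT, and it needs no calculation.

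**2. The plan's own figure.** Section 9.2 allows up to 30 patients in Part 1. The cohort ceilings give 6 + 8 + 8 + 8 = 30. That total needs Cohort 1 to expand to six after a DLT (Figure 1-1 note) and escalation then to continue. Under the literal Section 7.1.2 rule a DLT at 800 mg ends escalation, so the ceiling is 3 + 8 + 8 + 8 = 27. The sample size was therefore built on Section 4.1.1.

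**3. Size of the divergence, as illustration.** The documents give no assumed DLT rate, so the true rate p per patient is my assumption, taken over 5% to 20%. DLTs are treated as independent between patients. The patients added for PK are not modelled, although Section 4.1.1 applies the decision rule to them too.

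- Section 4.1.1 clears a level with 0/3, or with 1/3 followed by 0/3: (1−p)³ + 3p(1−p)² × (1−p)³
- A stop at any DLT clears it only with 0/3: (1−p)³

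| p | Section 4.1.1 | Any-DLT stop |
|---|---|---|
| 5% | 0.857 + 0.116 = 97.3% | 85.7% |
| 10% | 0.729 + 0.177 = 90.6% | 72.9% |
| 20% | 0.512 + 0.197 = 70.9% | 51.2% |

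If p were 10% at all four levels, the chance of clearing all four would be 0.906⁴ = 67.4% against 0.729⁴ = 28.2%.

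**4. What is known about p.** Section 4.2 reports no DLTs in the earlier EBRT study, which went up to 1200 mg with 15 patients at that dose. For 0/15 the exact 95% upper limit is 1 − 0.025^(1/15) = 21.8%. Across all 25 treated patients (Section 2.1) it is 1 − 0.025^(1/25) = 13.7%. A rate of 20% is therefore on the high side for 800 and 1200 mg if the two regimens are comparable. The earlier study did not test 1600 or 2400 mg.

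**5. The Section 7.1.1 trigger.** Every item on that list describes one patient, and no item has a count. Several are not safety events at all. Applied to a dose level without further words, the list does not tell the committee which items count, in how many patients or in which cycles.

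**The case against.** The best defence is that the intended rule is plain. The synopsis, Section 4.1.1, Table 3-1, Section 9.4.6.1 and the Figure 1-1 note all tolerate one DLT, and a single loosely drafted sentence stands against them. Section 7.1.2.1 also gives the committee the final decision on escalation and lets it expand the current level. The account of intent stands: this is very probably a cross-reference error, not a second design. It does not remove the conflict. Section 7.1.2 offers the committee its options only where stopping criteria are not met, Section 10.1.11 requires the protocol to be followed exactly, and Section 8 allows no waivers.

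It is also fair to say that the assumed rates may be too high at the lower doses, given no DLTs in the earlier study, and that the percentages are not full operating characteristics of either rule.

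A reader might go further and infer that one recurrent Grade 3 AE, or any Section 7.1.1 event, ends escalation, and might put a probability on it. The documents do not support that. On that reading one patient's withdrawal or progression would stop the study's escalation, which cannot be meant. The trigger speaks of safety criteria, Section 7.1.1 is permissive about stopping a patient, and local skin reactions that respond to topical corticosteroids are exempt. No recurrence rate is given anywhere. The committee's stated review set runs to Cycle 1 Day 21, and a related Grade 3 non-hematological event in that window is generally a DLT already.

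**Conclusion.** The point holds for the DLT trigger. As written, Section 7.1.2 contradicts Section 4.1.1 after exactly one DLT, and following it can give a lower RP2D from the same data. At assumed DLT rates of 5%, 10% and 20% the chance of clearing one level differs by 11.6, 17.7 and 19.7 percentage points. Those gaps rest on the assumed rates and leave out the PK patients; the contradiction rests on the wording alone.

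The reference to Section 7.1.1 is a secondary drafting defect: a list for individual patients used as a dose-level trigger. It should be corrected, but no numerical effect can be attached to it.

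A reader might also infer that patients are exposed to more risk. They are not: read literally, Section 7.1.2 errs toward stopping. The matter is worth correcting because it touches the primary objective and costs little, not because it undermines the design.

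**What to change.** Replace the first sentence of Section 7.1.2 with:

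> If the DLT count at a dose level meets the halting rule in Section 4.1.1 (> 1/3 or > 1/6 patients), no new patient starts at that level and escalation stops. Section 7.1.1 applies to individual patients. Before clearing a dose level the SSC must review any discontinuation for toxicity, any recurrent Grade 3 AE and any DLT-equivalent toxicity, and it may hold or stop that level.

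In the following sentence, change the opening condition to: *Where Section 4.1.1 does not require a halt*.

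The mandatory review keeps non-DLT safety events in front of the committee. If the sponsor wants such events to force a dose-level stop, the text should name the event, whether it must be related, the time window and the number of patients.

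Cost: two sentences in a protocol amendment, with matching wording in the SSC charter. No new data, visits or patients are needed.

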If the 1200 mg dose is not tolerable (i.e., 2 or more patients with DLTs), an additional 3 patients will be enrolled in the 800 mg dose cohort in order to declare 800 mg as the MTD (if no more than 1/6 patients experience a DLT).

If no DLT is observed at 2400 mg (Dose Cohort 4), dose escalation will be stopped. The proposed highest dose level (2400 mg) will be declared the RP2D.

There will be a temporary halt for enrollment after the first 3 patients are enrolled in each cohort until the SSC clears that the dose level is safe to continue the dose escalation. During the SSC meeting for NOX66 dose escalation decision, the safety and tolerability of both EBRT doses (8 Gy and 20/25 Gy) will also be evaluated. For details on DLT evaluation, see Section 7.1.2.2.

DLT monitoring will be applicable for all patients enrolled in each cohort, including patients enrolled for the purpose of PK analysis; as well as the decision rule for the additional PK patients (i.e., stopping dose escalation).

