4.2 Scientific Rationale for Study Design

Better SOC treatments for patients with prostate cancer and patients with other solid tumors, who have exhausted treatments, are needed. Based on the positive results observed in Phase 1 clinical studies with NOX66, further investigation is warranted.

The study is divided into 2 parts: Part 1 (dose escalation) and Part 2 (dose expansion). During Part 1, four dose levels of NOX66 will be examined to determine the MTD and RP2D to be used in further clinical development of NOX66. In Part 2, the confirmed RP2D dose level will be further examined in patients with mCRPC, BC and NSCLC. Part 2 will also examine the effect of NOX66 on PSA of patients with mCRPC and the tumor response in patients with BC and NSCLC.

Radiotherapy (i.e., low-dose EBRT) will be provided to patients during this study. Low-dose EBRT is administered for the treatment of symptomatic lesions and/or to prevent asymptomatic lesions from becoming symptomatic. Low-dose EBRT (8 Gy or 20/25 Gy as 1 or 5 fractionated doses, respectively) will be administered in this study for symptom control of lesions and

prevention of signs and symptoms. The safety of the combination of NOX66 and EBRT has been tested in men with symptomatic mCRPC¹ (see IB² for details).

The starting dose, dose escalation decision points and patient population size are based on accepted methodology for Phase 1/Phase 2 studies.

In the previous study (NOX66-002A), the doses of 400 mg, 600 mg, 800 mg and 1200 mg of NOX66 were explored in combination with low-dose EBRT in patients with mCRPC. The highest dose tested in this study was 1200 mg and a total of 15 patients have been treated with this dose. There were no DLTs reported in that study. Based on the NOX66-002A study safety and efficacy data this planned study is designed to continue the dose escalation from 800 mg (400 mg BID) to 1200 mg (600 mg BID) to 1600 mg (800 mg BID) followed by 2400 mg (1200 mg BID), if tolerable.

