4.3 Justification for Dose

The selected starting dose, 800 mg NOX66 (total dose; 400 mg BID), has been used in a previous clinical trial (NOX66-002A) and was shown to be safe and well tolerated. This dose level is the possible lowest BID dose of NOX66.

Low-dose EBRT (8 Gy or 20/25 Gy given as 1 or 5 fractionated doses, respectively) is considered SOC in this patient population. The choice of dose/fraction is at Investigator's discretion based on patient's need. Site will need to follow institutional practice for low-dose EBRT administration.

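### Section 7.1.2 bars repeating or escalating a dose once a DLT is seen, with no patient count, which conflicts with the 3+3 rule stated elsewhere in the protocol

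*Combined protocol and SAP*

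**What the plan says.** Section 7.1.2, which is headed as the dose escalation rules, names two triggers. The first is "A dose in which the safety stopping criteria have been met (Section 7.1.1"), and the second applies to a dose "where toxicity was observed based on the DLT assessment criteria (Section 7.1.2.2) will not be repeated and further dose escalation will not occur". The SSC's choices, which include repeating a dose, open only in the opposite case: "Where stopping criteria have not been met, the decision of the SSC may be to give the next intended dose". Section 7.1.2.2 defines a DLT as an event in one patient during Cycle 1, says who is evaluable, and requires at least three evaluable patients per cohort. It states no number of DLTs that closes a dose.

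Section 4.1.1 sets out an adapted 3+3 design, and the synopsis repeats it. "If 1/3 patients experience a DLT, an additional 3 patients will be enrolled", all at the same dose. One in six makes the level safe and opens the next one. "If > 1/3 or > 1/6 patients experience a DLT, then dose escalation will be halted". DLT monitoring also covers patients added for pharmacokinetics, "as well as the decision rule for the additional PK patients (i.e., stopping dose escalation").

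Other places agree with 4.1.1:

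- The Figure 1-1 note allows up to three more patients in Cohort 1 if a DLT occurs.
- The synopsis, Table 3-1 and Section 9.4.6.1 accept one DLT in six patients when defining the MTD and RP2D.
- Section 7.1.2.1 lets the SSC expand the current level.
- Section 7.1.2.2 has the CRO look for a second DLT after a first.

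**The concern.** Part 1 exists to find the MTD and RP2D, and the rule for stopping escalation determines both. A first DLT is the ordinary event that a 3+3 design is built to handle, and it is where the two texts part. After one DLT in three patients, 4.1.1 tells the SSC to treat three more at that dose, while 7.1.2 as worded forbids it. The route from one in three to one in six then cannot be completed.

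The error is in the cautious direction. A literal reader stops early and may carry too low a dose into Part 2, where every patient receives the RP2D. At 800 mg the effect would be sharpest, because Section 4.3 says of it: "This dose level is the possible lowest BID dose of NOX66". No lower level is planned.

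**Working it through.** **The plan's own figure.** Maximum Part 1 size = 6 (Cohort 1) + 3 × 8 (Cohorts 2 to 4) = 30, which matches Section 9.2. Cohort 1 reaches six patients only by expanding after a DLT, or under the 4.1.1 provision for adding three patients at 800 mg if 1200 mg proves intolerable.

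**The two rules by DLT count at a dose level**

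| Observed | Section 4.1.1 | Section 7.1.2, literal |
|---|---|---|
| 0 of 3 | Escalate | Escalate |
| 1 of 3 | Treat 3 more at this dose | Do not repeat; stop escalating |
| 1 of 6 | Safe; open next level | Cannot be reached if the DLT is in the first 3 |
| 2 or more | Halt | Stop |

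They differ only when a level has exactly one DLT.

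**Inputs.** The documents give no true DLT rate, so p = 2%, 5%, 10% and 20% per patient are assumptions. For scale, Section 4.2 reports no DLTs in the earlier study and says "The highest dose tested in this study was 1200 mg and a total of 15 patients have been treated with this dose". For 0 of 15, the exact two-sided 95% upper limit is 1 − 0.025^(1/15) = 21.8%, so the four rates lie inside 0% to 21.8%. The earlier schedule differed, its DLT definition is not given, and nothing there covers 1600 or 2400 mg.

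**Decision on three, then six, patients**

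- 4.1.1 clears the dose: (1−p)³ + 3p(1−p)² × (1−p)³
- Literal 7.1.2 clears it: (1−p)³
- Difference: 3p(1−p)⁵

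| p | 4.1.1 clears | Literal 7.1.2 clears | Difference |
|---|---|---|---|
| 2% | 99.5% | 94.1% | 5.4% |
| 5% | 97.3% | 85.7% | 11.6% |
| 10% | 90.6% | 72.9% | 17.7% |
| 20% | 70.9% | 51.2% | 19.7% |

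At 10%, for example, 3 × 0.10 × 0.9⁵ = 0.177. If 10% held at three successive levels, the chance of clearing all three would be 0.906³ = 74.4% against 0.729³ = 38.7%.

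**If a cohort in 2 to 4 fills to eight.** Section 4.1.1 gives no count out of eight. A halt at two or more is inferred: 1/8 = 12.5% is below 1/6 = 16.7%, 2/8 = 25% is above it, and 4.1.1 calls 1200 mg intolerable at two or more patients with DLTs.

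- One-DLT bar: 1 − (1−p)⁸ = 14.9%, 33.7%, 57.0%, 83.2%
- 4.1.1 halt, two or more of eight: 1.0%, 5.7%, 18.7%, 49.7%
- Difference, exactly one of eight: 8p(1−p)⁷ = 13.9%, 27.9%, 38.3%, 33.6% (from unrounded values)

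**The case against.** The best reply is that nobody would follow 7.1.2 literally. Its subject is a dose, and 7.1.2.2 treats DLT evaluation as a cohort exercise, so toxicity observed can be read as a dose found toxic on cohort review. The Figure 1-1 note points to 4.1.1 and 7.1.2.2 together for DLT assessment, and 4.1.1 itself refers to 7.1.2.2. The threshold is repeated in the synopsis, Table 3-1 and Section 9.4.6.1. The SSC has the final decision and may expand a level.

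All of that stands as evidence of intent. It does not remove the conflict, because the softer reading needs a count that neither 7.1.2 nor the section it cites supplies. The Figure 1-1 provision for three more patients in Cohort 1 is itself something literal 7.1.2 would forbid. No order of precedence is stated, while Section 10.1.11 requires exact adherence and Section 8 rules out waivers.

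Three stronger readings are tempting and should not be drawn:

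- **The design is unclear, or patients are at added risk.** The 4.1.1 design is clear, and the stray wording leads to less exposure.
- **The eight-patient differences apply throughout.** Enrolment to eight is optional, and no level lies above Cohort 4, so a bar on escalation means little there.
- **Any item in 7.1.1, such as loss to follow-up, would close a dose level.** Section 7.1.2 refers to safety stopping criteria, and 7.1.2.2 and 7.2 allow replacement of patients who leave Cycle 1 for non-safety reasons.

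**Conclusion.** The conflict is real but confined to wording. Section 7.1.2 states a stopping rule without a patient count, and followed as written it contradicts the 3+3 rule and the one-in-six definition used everywhere else. Section 4.1.1 is plainly intended and would probably prevail in the SSC, so an RP2D set too low is possible rather than likely.

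If 7.1.2 were applied literally, the chance of barring a dose that 4.1.1 clears would be about 5% to 20% per level at the three-to-six decision, for assumed DLT rates of 2% to 20%. The figures of 14% to 38% need a full cohort of eight and the inferred halt at two or more. All these figures treat patients as independent with a common DLT rate. That the two texts conflict does not depend on any of them.

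The reference to 7.1.1 is a lesser fault: that list gives reasons for stopping one patient and has no dose-level count or window.

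**What to change.** At the next amendment, rewrite the sentence in 7.1.2. Replace its DLT limb with: where > 1/3 or > 1/6 patients (2 or more patients at a dose level) experience a DLT per Section 4.1.1, including additional PK patients. In the same sentence, drop 7.1.1 as a trigger for closing a dose level.

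Retitling 7.1.1 as individual discontinuation criteria, restating the replacement rule, or adding a counted non-DLT trigger with a Day 1 to 21 window would be optional.

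The cost is one sentence. Sample size, procedures and analyses do not change.
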